8.0 RESPONSE CRITERIA

A 4-week period after the first infusion will constitute a course, which will be evaluated for critical toxicity.

Patients with measurable disease will be assessed by standard criteria to determine clinical response. Evaluations of tumor size will be performed pre-infusion and approx. every 2-3 months thereafter as per standard clinical care patient monitoring. All patients who receive multiTAA T cells and continue to be enrolled on the study will be evaluable for response. Patient long term overall and progression free survival will also be evaluated at 1 year and then annually for up to an additional 4 years (total of 5 years follow-up).

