5.2 Administration and Monitoring

Three disease groups will be studied.

Group A: Patients with locally advanced or metastatic adenocarcinoma who are responding (defined as stable disease or tumor volume reduction) following 3 cycles of first line chemotherapy will be evaluated in the clinic and receive 6 infusions with a fixed dose of multiTAA T cells starting on chemotherapy cycle 4 and occurring on the 4th week of the cycle, which is a chemotherapy “off” week.

Group B: Patients with locally advanced or metastatic adenocarcinoma who have failed first line chemotherapy or are intolerant or ineligible to receive standard of care chemotherapy will be evaluated in the clinic and receive 6 infusions (administered at monthly intervals) with a fixed dose of multiTAA T cells.

Group C: Patients with resectable pancreatic adenocarcinoma following completion of neoadjuvant chemotherapy, radiotherapy or combination. These patients will receive 6 infusions with a fixed dose of multiTAA T cells. One infusion will occur 4 weeks prior to surgical resection (with an option to infuse up to one week earlier) and after the completion of all pre-operative chemotherapy and/or radiation. The subsequent 5 infusions will occur at monthly intervals beginning 8 weeks post-surgery.

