Monitoring: Patients will be monitored for clinical toxicity by the CTEP NCI Common Toxicity Criteria Scale (Version 4.X, See Section 12.3) with the exception of CRS toxicities that are related to T cell infusions. CRS toxicities will be graded according to Appendix I. We will also analyze immunological parameters including T cell frequencies by ELIspot and multimer studies in patients who have HLA types for which multimers are available. Functional analyses (antigen-specific cytotoxicity and cytokine release) will be performed by chromium release assays and ELIspot/intracellular cytokine staining, respectively. The levels of serum cytokines before and following infusion will be compared. A time period of 4 weeks post the 1st infusion will constitute the time for clinical efficacy and safety monitoring. Thereafter patients will receive 5 additional infusions of cells at the same cell dose (or below the patient's original dose can be administered) at monthly intervals. Patients that undergo surgical resections (Group C) will receive 1 infusion prior to surgery and 5 additional infusions of cells at the same cell dose (or below the patient's original dose can be administered) at monthly intervals after surgery.

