7.0 PATIENT EVALUATION

7.1 Follow-up Interval

Patients shall be seen in clinic prior to each T cell infusion and evaluated (seen in clinic or contacted by research coordinator) at 1 and 2 weeks after each infusion, week 4, 6, and 8 after the last infusion and then at 3, 6, 9 and 12 months after the last infusion. Study-related blood draws will cease 12 months after the last T cell infusion but we will then continue to follow patients clinically for up to 4 additional years (total of 5 years follow-up) to evaluate long-term disease responses. If persistence of cells is noted at the 12 month visit, additional follow up will be added. Additional visits will be obtained as clinically indicated.

- 7.2 A complete history and physical examination is necessary prior to administration of multiTAA T cells. Medical history will be obtained at every follow-up visit and will be reviewed annually for 5 years.

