7.3 Other Studies

- 7.3.1 The following investigations will be obtained at the time points specified in the study calendar:
CBC and differential, BUN, creatinine, bilirubin, SGOT, SGPT, alkaline phosphatase, Na, K, Cl, CO₂, albumin and total protein, and CA19-9.
- 7.3.2 Pregnancy testing (blood) is required on female patients of childbearing potential prior to multiTAA T cell infusion #1.
- 7.3.3 Diagnostic imaging (CT scans, MRI, nuclear imaging) and/or blood tests (serum cytokines) to document measurable disease and response to therapy prior to the first infusion and every 2-3 months thereafter for up to 1 year after the last infusion, as per standard clinical care monitoring for patients with pancreatic cancer. The time may vary by 1-2 weeks due to scheduling issues and may be done earlier if clinically indicated. If diagnostic imaging studies are performed at other times either during or after treatment on this study, that data will be collected and information gained will be used for this study.
- 7.3.4 The following investigations will be obtained at the time points specified in the study calendar. 20-40ml of peripheral blood will be collected in preservative-free heparin.. This blood will be used for analysis of specificity of multiTAA T cell response using HLA multimer analysis and immune function assays including ELIspot, intracellular cytokine staining and cytotoxicity assays. Serum will be batched for analysis of blood cytokine levels. These studies will be done on patients on whom the appropriate reagents are available.
- 7.3.5 Study specific blood tests will cease 12 months after the last T cell infusion but we will continue to follow patients clinically once a year for up to 4 additional years (total of 5 years follow-up) to evaluate long term disease responses.
- 7.3.6 Other Tissues: Should the patient undergo a tumor biopsy/surgical resection at any time while they are on study, a sample of this will be used to assess the tumor antigen expression profile and to look for evidence of T cell infiltration.
- 7.3.7 If a patients' hemoglobin is <7.0g/dl at any of the evaluation times, the amount of blood drawn for the evaluation will be reduced and may be obtained over more than one venipuncture, if necessary.

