7.4 Summary of Monitoring

Group A Study week	Pre- Infusion	Treatment	Wk1	Wk2	Wk3	Wk4	Wk5	Wk6	Wk7	Wk8	Wk9	Wk10	Wk11
Events			SOC	SOC	SOC		SOC	SOC	SOC		SOC	SOC	SOC
T cells		x				x				x			
History	X		x	x		x	x	x	x	x	x	x	
Physical	X					x				x			
CBC/diff	X					x				x			
BUN, creatinine, bilirubin, SGOT, SGPT, alkaline phosphatase, Na, K, Cl, CO ₂ , albumin, total protein, CA 19-9 ^s	X					x				x			
Imaging [^]	X												
Immune Function [↓]	X		x	x		x	x	x		x	x	x	
Pregnancy test [#]													

Group A Study week	Wk12	Wk13	Wk14	Wk15	Wk16	Wk17	Wk18	Wk19	Wk20	Wk21	Wk22*
Events		SOC	SOC	SOC		SOC	SOC	SOC		SOC	SOC
T cells	x				x				x		
History	x	x	x		x	x	x		x	x	x
Physical	x				x				x		
CBC/diff	x				x				x		
BUN, creatinine, bilirubin, SGOT, SGPT, alkaline phosphatase, Na, K, Cl, CO ₂ , albumin, total protein, CA 19-9 ^s	x				x				x		
Imaging [^]											
Immune Function [↓]	x	x	x		x	x	x		x	x	x
Pregnancy test [#]											

Group B Study week	Pre- Infusio n	Treatment	Wk 1	Wk2	Wk3	Wk4	Wk5	Wk6	Wk7	Wk8	Wk9	Wk10	Wk11
T cells		x			x				x				
History	x		x	x		x	x	x	x	x	x	x	
Physical	x					x			x				
CBC/diff	x					x			x				
BUN, creatinine, bilirubin, SGOT, SGPT, alkaline phosphatase, Na, K, Cl, CO ₂ , albumin, total protein, CA 19-9 ^s	x					x			x				
Imaging [^]	x												
Immune Function ⁺	x		x	x		x	x	x	x	x	x	x	
Pregnancy test [#]	x												

Group B Study week	Wk12	Wk13	Wk14	Wk15	Wk16	Wk17	Wk18	Wk19	Wk20	Wk21	Wk22*
T cells	x				x				x		
History	x	x	x		x	x	x	x	x	x	x
Physical	x				x			x			
CBC/diff	x				x			x			
BUN, creatinine, bilirubin, SGOT, SGPT, alkaline phosphatase, Na, K, Cl, CO ₂ , albumin, total protein, CA 19-9 ^s	x				x			x			
Imaging [^]											
Immune Function ⁺	x	x	x		x	x	x		x	x	x
Pregnancy test [#]											

Group C Study week	Pre- Infusio n	Treatm ent [§]	Wk1	Wk 2	Wk 3	Wk4	Infusi on #2 [%]	Wk1	Wk 2	Wk 3	Wk 4	Wk 5	Wk 6	Wk 7
Events						Surgery		SO C	SO C	SO C		SO C	SO C	SO C
T cells		x					x				x			
History	x		x	x			x	x	x		x	x	x	
Physical	x						x				x			
CBC/diff	x						x				x			
BUN, creatinine, bilirubin, SGOT, SGPT, alkaline phosphatase, Na, K, Cl, CO ₂ , albumin, total protein, CA 19-9 [§]	x						x				x			
Imaging [^]	x													
Immune Function [⊥]	x		x	x			x	x	x		x	x	x	
Pregnancy test [#]	x													

Group C Study week	Wk8	Wk9	Wk10	Wk11	Wk12	Wk13	Wk14	Wk15	Wk16	Wk17	Wk18*
Events		SOC	SOC	SOC							
T cells	x				x			x			
History	x	x	x		x	x	x	x	x	x	
Physical	x				x			x			
CBC/diff	x				x			x			

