BUN, creatinine, bilirubin, SGOT, SGPT, alkaline phosphatase, Na, K, Cl, CO ₂ , albumin, total protein, CA 19-9 [§]	x				x			x			
Imaging [^]											
Immune Function [⊥]	x	x	x		x	x	x		x	x	x
Pregnancy test [#]											

Generic Long term follow-up Table

Study timepoint (after last infusion)	Wk4	Wk6	Wk8	Mth 3, 6, 9, 12	Yr 2, 3, 4, 5
T cells					
History	x	x	x	x	x
Physical					
CBC/diff					
BUN, creatinine, bilirubin, SGOT, SGPT, alkaline phosphatase, Na, K, Cl, CO ₂ , albumin, total protein, CA 19-9 [§]					
Imaging [^]					
Immune Function [⊥]	x	x	x	x	
Pregnancy test [#]					

SOC = Standard of care

* Following this study time point monitoring will be performed per long term follow-up Table & For Group C the 1st infusion occurs at 4 weeks prior to surgery with a provision to infuse up to 1 week earlier to allow for variations in surgery scheduling.

% For Group C the 2nd infusion will occur 8 weeks post-surgery

[^]See Section 7.3.3. Imaging studies can be performed within 8 weeks of T cell administration and post-infusion monitoring will be per standard of care

[⊥] See Section 7.3.4

[#] See Section 7.3.2

\$ Or any other serum tumor marker that is elevated because of the pancreatic tumor (such as CEA or CA-125)

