9.4. Stopping Guidelines

Statistical monitoring of grade III-IV CTCAE toxicity or grade 3-4 CRS toxicities related to T cells is employed. Safety guideline and the rule for halting the accrual will be implemented separately for each cohort. The guidelines serve as a trigger for consultation with the FDA for additional review, and are not formal "stopping rules" that would mandate automatic closure. Additionally, after consultation with the FDA, the PI can stop the study early.

In Group C, it is extremely unlikely that patients who receive their first T cell infusions will not undergo surgical resection since all imaging studies and a clinical plan will be determined prior to infusion and it is unlikely that the T cells will cause inflammation precluding/delaying subsequent surgical resection. The accrual to Cohort C will be halted if any patient experiences a delay in subsequent surgical resection due to toxicity related to the T-cell infusion and this issue will be discussed with the FDA to develop a plan. The plan would be submitted to the DRC and IRB prior to resuming accrual to Cohort C.

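### In Group C no physical examination, CBC or chemistry is scheduled between the pre-infusion visit and infusion 2, 12 to 13 weeks after infusion 1, so none falls inside the 4-week toxicity course or before surgery

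*Combined protocol and SAP*

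**What the plan says.** Two sections make the first 4 weeks the safety window, without distinguishing the groups. Section 8.0: "A 4-week period after the first infusion will constitute a course, which will be evaluated for critical toxicity". Section 5.2: "A time period of 4 weeks post the 1st infusion will constitute the time for clinical efficacy and safety monitoring".

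Group C timing comes from 5.2 ("One infusion will occur 4 weeks prior to surgical resection (with an option to infuse up to one week earlier") and from a footnote to 7.4 ("For Group C the 2nd infusion will occur 8 weeks post-surgery").

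Section 7.1 has patients "evaluated (seen in clinic or contacted by research coordinator) at 1 and 2 weeks after each infusion". The blood taken at the immune-function time points is described in 7.3.4 ("20-40ml of peripheral blood will be collected in preservative-free heparin") and is for T-cell assays and serum cytokines. CBC and chemistry are a separate item (7.3.1), obtained when the calendar says so.

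Section 9.3.4 plans descriptive laboratory summaries before infusion, at weeks 1, 2, 4, 6 and 8, and at months 3 to 12 after infusion, for each disease group. Section 9.4 adds a rule for this group alone, tied to toxicity from the T cells: "The accrual to Cohort C will be halted if any patient experiences a delay in subsequent surgical resection due to toxicity related".

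**The concern.** The primary safety endpoint counts T-cell-related grade III-IV CTCAE toxicity or grade 3-4 CRS (9.1). Appendix I puts grade 3 organ toxicity and grade 4 transaminitis within CRS grade 3. Several such events are recognised or graded from laboratory values or an examination, not from a history.

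In Groups A and B those values are scheduled at week 4, the end of the course. In Group C week 4 is the operation, and nothing replaces the visit. The first scheduled safety laboratory values after T-cell exposure come 8 weeks after major surgery, when an abnormality is hard to attribute. Two events halt accrual to the group (9.2), so a single missed or misattributed event can change the decision. The 9.4 surgery-delay rule turns on attribution to T cells, which is the judgement that a pre-surgical assessment would inform. Section 3.6 makes this more than theoretical: it reports pancreatitis in treated patients on this study and does not rule out a role for the T cells.

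**Working it through.** **Step 1. Read the calendar.** In the first table headed "Group C Study week" (7.4), the marks from the pre-infusion visit to infusion 2 are:

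| Item | Pre | Infusion 1 | Wk 1 | Wk 2 | Wk 3 | Wk 4 | Infusion 2 |
|---|---|---|---|---|---|---|---|
| Event | | | | | | Surgery | |
| T cells | | x | | | | | x |
| History | x | | x | x | | | x |
| Immune function | x | | x | x | | | x |
| Physical | x | | | | | | x |
| CBC/diff | x | | | | | | x |
| Chemistry, CA 19-9 | x | | | | | | x |

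The columns line up across all rows, so this does not look like a text-extraction fault. Within the 4 weeks after infusion 1, physical, CBC and chemistry have 0 marks; history and immune function have 2 each. The Group A and Group B tables mark physical, CBC and chemistry at week 4.

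**Step 2. Length of the gap.** Inputs: infusion 1 to surgery, 4 weeks or up to 5 (5.2); surgery to infusion 2, 8 weeks (7.4 footnote).

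- Infusion 1 to infusion 2: 4 + 8 = 12 weeks, up to 5 + 8 = 13 weeks.
- Time with no calendar assessment after week 2: 12 − 2 = 10 weeks, up to 13 − 2 = 11 weeks.
- Patients affected: up to 15 of 45, one third.

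**Step 3. Compare with 9.3.4.** After infusion 1, Group C has no CBC or chemistry at week 1, 2 or 4. The week 4 gap is specific to Group C. Groups A and B also lack these tests at weeks 1 and 2, so that part of the conflict is general. Section 9.3.4 does not say which infusion the weeks are counted from. Counting from the last infusion does not remove the conflict, because the long-term follow-up table leaves the CBC and chemistry rows blank at weeks 4, 6 and 8 and at months 3 to 12.

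**Step 4. Patients whose first infusion is their last.** They move to the long-term table. It gives history and immune function at weeks 4, 6 and 8 and at months 3 to 12, but physical, CBC and chemistry are blank throughout.

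**Step 5. What depends on event capture.** The 9.2 rule halts a group at more than 1 event in 15 patients. With X the number of events, P(X ≥ 2) = 1 − (1 − p)^15 − 15p(1 − p)^14.

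- p = 0.20: 1 − 0.0352 − 0.1319 = 0.8329. The plan states 83.3%; reproduced.
- p = 0.015: 1 − 0.7972 − 0.1821 = 0.0208. The plan states 2.08%; reproduced.

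These figures assume that every event is seen. The documents give no capture rate, so the following range is an assumption used only to show sensitivity:

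| Share of events captured | Effective p | Power |
|---|---|---|
| 100% | 0.20 | 83.3% |
| 90% | 0.18 | 78.1% |
| 75% | 0.15 | 68.1% |
| 50% | 0.10 | 45.1% |

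The gap concerns the interval after infusion 1, while the rule counts events over all infusions, so no row is an estimate for this trial.

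**The case against.** The plan has other routes to safety data. Adverse events of any seriousness are collected until 8 weeks after the last dose (12.3.3). Extra visits take place when clinically indicated (7.1). Chemistries, hematologic parameters, clinical status and surgical summaries are to be kept on all patients (11.0). A toxicity serious enough to postpone an operation would very probably surface this way, and pre-operative tests are likely in practice. All of this stands, and it rules out several stronger readings that a reader might infer:

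- *The 4-week course has no visit or blood draw behind it.* It has history and a research sample at weeks 1 and 2. The limits are that the contact may be by coordinator only and that the sample is not for safety chemistry.
- *The 9.4 rule has no data.* A delay is observable and adverse events are recorded. What is missing is a scheduled pre-surgical assessment to support attribution.
- *A patient who is not resected drops out of follow-up.* The long-term table keeps history and immune contacts; only the examination and safety laboratory rows are blank.
- *The Group C safety result is biased downward.* Under-capture is plausible, but nothing in the documents shows how many grade 3-4 events would be silent at week 2 and also absent from peri-operative records.
- *Only Group C shows T-cell exposure free of other treatment.* Group B must be off conventional therapy before treatment (4.3.10), and its calendar shows neither surgery nor standard-of-care events.
- *The resection specimen needs a matched blood sample.* Neither 7.3.6 nor 9.3.3 plans a paired analysis.

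The alternative routes still leave a gap. They act on symptoms or on care given for other reasons, and none schedules a test for a silent toxicity or requires pre-operative values to be captured at a defined time.

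**Conclusion.** The point holds as a calendar gap and an internal inconsistency. Followed exactly, the plan yields no scheduled physical examination, CBC or chemistry in Group C for 12 to 13 weeks after infusion 1. There is none within the toxicity course set by 5.2 and 8.0 and none before surgery, and the laboratory summaries in 9.3.4 have no matching draws. It affects up to 15 patients. Its effect on the count of treatment-related events is of unknown size and may be small if peri-operative records are complete. It is worth correcting because two events halt the group and the correction is cheap; it does not invalidate the safety design. The conclusion rests on the Group C table having been read correctly and on no other scheduled source of these tests existing in the documents.

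**What to change.** Reconcile 5.2, 7.4, 8.0, 9.3.4 and 9.4 as follows:

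- Add to the Group C calendar an end-of-course data point before surgery, marked for history, physical, CBC and chemistry. Allow pre-operative work-up values to fill it, assuming that a work-up is done.
- Name it in 8.0 as the end of the Group C course, in 9.3.4 as the Group C week 4 laboratory time point, and in 9.4 as a data source for the surgery-delay decision.
- State in 9.3.4 which infusion its weeks are counted from, and align the week 1 and 2 laboratory time points, and those after the last infusion, with the calendar. Where no draw is intended, remove the time point from the analysis.
- State what safety laboratory data, if any, are expected from a patient whose first infusion is the last.

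The cost is a calendar amendment, data entry, and possibly one set of blood tests for each of up to 15 patients. No treatment changes.

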8.1 Definitions

This study will use the RECIST 1.1 criteria

Definitions

Response and progression will be evaluated in this study using the international criteria proposed by the Response Evaluation Criteria in Solid Tumors (RECIST 1.1) Committee. Changes in only the largest diameter (unidimensional measurement) of the tumor lesions are used in the RECIST criteria. Measurable lesions are defined as those that can be accurately measured in at least one dimension (longest diameter to be recorded) as >10 mm with CT scan, MRI, or clinically using calipers. The investigator will identify up to 5 measurable lesions to be followed for response. Serial measurements are to be done with CT or MRI. The same method of assessment is to be used to characterize each identified and reported lesion at baseline and during follow-up.

Complete Response: Disappearance of all target lesions

Partial Response (PR): At least a 30% decrease in the sum of the longest diameter (LD) of target lesions, taking as reference the baseline sum LD

Progressive Disease (PD): At least a 20% increase in the sum of the LD of target lesions, taking as reference the smallest sum LD recorded since the treatment started or the appearance of one or more new lesions

Stable Disease (SD): Neither sufficient shrinkage to qualify for PR nor sufficient increase to qualify for PD, taking as reference the smallest sum LD since the treatment started

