9.3 Statistical Analysis

9.3.1 Safety Analysis of Toxicity and Adverse Event Data

All patients who receive at least one infusion of multiTAA-specific T cells will be included in the safety analysis. Patients will be monitored for clinical toxicity by the CTEP NCI Common Toxicity

Criteria Scale (Version 4.X, See Section 12.3) with the exception of CRS toxicities that are related to T cell infusions. CRS toxicities will be graded according to Appendix I.

Adverse event data and corresponding toxicity grades after T cell infusions and during long-term follow-up will be summarized in the form of tables. Incidence tables will be generated to summarize incidence of patients reporting at least one episode of each specific adverse event, incidence of adverse events causing withdrawal and incidence of serious adverse events. The total number of episodes for each event reported (Frequency Table), the severity and attribution to study therapy of each episode reported (Severity Table and Attribution Table) will also be calculated.

Listings of adverse events by patients will include the time to onset, the duration of each event, the severity of each event, and the relationship of the event to study therapy, whether it was a serious event, and whether it caused withdrawal. Safety data will be summarized for each patient group and for all treated patients.

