9.3.2. Analysis of anti-tumor activity, progression-free and overall survival data

Although tumor response and survival are not the primary endpoint of this trial, we will summarize tumor response by calculating overall response rates along with exact 95% binomial confidence intervals. Response will be evaluated as described in section 8.4. The progression-free and overall survival of patients will be summarized using the Kaplan-Meier method. The analysis will be done for each patient group and for all treated patients. We will also explore the relationship between the patient baseline characteristics and response as well as PFS/OS based on eth logistic model and the Cox regression methods, respectively.

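### Section 8.0 makes response evaluability depend on staying on study, and Section 9.3.2 pools resected Group C without saying how removed lesions count (minor)

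*Combined protocol and SAP*

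**What the plan says.** **Who is evaluable.** Section 8.0 states: "All patients who receive multiTAA T cells and continue to be enrolled on the study will be evaluable for response". The off-study reasons in Section 10.2 include death, withdrawal of consent and loss to follow-up. Patients who only stop treatment move to modified follow-up under Section 10.1, and their response data are still collected.

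**What is reported.** Section 9.3.2 plans overall response rates with exact 95% binomial intervals, and Kaplan-Meier summaries of progression-free and overall survival. It then says: "The analysis will be done for each patient group and for all treated patients". It adds: "Response will be evaluated as described in section 8.4". The supplied text of Section 8 contains only 8.0 and 8.1.

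**How response is defined.** Section 8.1 says: "This study will use the RECIST 1.1 criteria". Its own summary includes "Complete Response: Disappearance of all target lesions", and defines partial response as a fall of at least 30% in the summed longest diameters from baseline. It does not mention lesions removed by surgery.

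**Group C.** Section 5.2 places infusion 1 four weeks before resection, or up to one week earlier than that. Section 9.4 says "it is extremely unlikely that patients who receive their first T cell infusions will not undergo surgical resection", because "all imaging studies and a clinical plan will be determined prior to infusion". Section 7.3.3 requires imaging before infusion 1 and then every 2 to 3 months, with a 1 to 2 week tolerance.

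**Contrast with safety.** Section 9.3.1 has an explicit population: "All patients who receive at least one infusion of multiTAA-specific T cells will be included in the safety analysis". Response has no equally clear rule.

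**The concern.** A patient who leaves before any post-baseline scan cannot be a documented responder. Taking such patients out of the denominator makes the analysis set depend on what happened after treatment, and it can move the rate in one direction only. Some early loss is plausible: Section 4.3.3 asks for a life expectancy of at least 12 weeks at treatment entry, and the first routine scan falls at about 9 to 13 weeks.

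In Group C, the first routine scan after infusion may come after the target lesions have been removed. If those patients are scored as responders, the Group C rate measures surgery and lifts the pooled rate. If they are not, but stay in the pooled denominator, patients who may have had no opportunity to show a response dilute it. In both cases the pooled figure depends on a convention that the protocol's own text does not state. What is at stake is a misleading descriptive result; no trial decision is affected.

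**Working it through.** The plan states no expected response rate, so there is no figure of its own to reproduce here. Group size (at most 15) and total (at most 45) come from Section 9.1. All counts of responders, early leavers and resections scored as response are assumptions. Intervals are exact (Clopper-Pearson), the type named in 9.3.2.

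**1. Denominator.** With *n* treated, *r* responders and *d* leaving before a post-baseline scan, the literal 8.0 rate is r/(n − d), which is never below r/n.

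- d = 0: 3/15 = 20.0% (4.3 to 48.1)
- d = 1: 3/14 = 21.4% (4.7 to 50.8)
- d = 5: 3/10 = 30.0% (6.7 to 65.2)
- r = 0: 0% for any d

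**2. Does the first Group C scan precede surgery?** Surgery is at week 4 to 5 after infusion 1. Two months is 8.7 weeks and three months is 13.0 weeks.

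- Interval counted from infusion 1: the earliest routine scan is 8.7 − 2 = week 6.7, after surgery.
- Interval counted from a baseline scan *b* weeks before infusion 1 (the Section 7.4 footnote allows 8 weeks): the scan precedes surgery when b > interval − tolerance used − surgery week.
 - Two-month interval: b > 8.7 − 5 = 3.7 to 8.7 − 4 = 4.7 with no tolerance used, or b > 1.7 to 3.7 if done 1 to 2 weeks early.
 - Three-month interval: b > 8.0 to 9.0 with no tolerance used, outside the window; b > 6.0 to 8.0 if done 1 to 2 weeks early.

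A pre-surgery scan is therefore possible but not assured.

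**3. Pooled rate.** With *r* responders among 30 in A and B, and *c* of 15 in C scored as complete response because of resection, the pooled rate is (r + c)/45. Each such patient adds 1/45 = 2.2 points.

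| A and B | c = 0 | c = 8 | c = 15 |
|---|---|---|---|
| 0/30 = 0% | 0/45 = 0% | 8/45 = 17.8% | 15/45 = 33.3% |
| 3/30 = 10% | 3/45 = 6.7% | 11/45 = 24.4% | 18/45 = 40.0% |
| 6/30 = 20% | 6/45 = 13.3% | 14/45 = 31.1% | 21/45 = 46.7% |
| 9/30 = 30% | 9/45 = 20.0% | 17/45 = 37.8% | 24/45 = 53.3% |

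The pooled rate exceeds the A and B rate when (r + c)/45 > r/30, that is when c > r/2. At r = 6 the direction changes at c = 3. The dilution example with intervals: 6/30 = 20.0% (7.7 to 38.6) becomes 6/45 = 13.3% (5.1 to 26.8).

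**4. Progression after resection.** Section 8.1 measures progression as a 20% rise over the smallest sum of diameters. If resection brings that sum to zero, the percentage is undefined, and only the new-lesion part of the definition can be applied.

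**The case against.** **On the denominator.** A reader might infer that 8.0 and 9.3.2 contradict each other. The documents do not support that. The response-rate sentence in 9.3.2 gives no denominator, and its closing reference to everyone treated most naturally names the pooled stratum; 9.3.1 uses the same phrase in that way for safety summaries. The 8.0 sentence may itself only describe who goes on being assessed. Early loss is also limited: Section 4.1.2 asks for at least 6 months' life expectancy at procurement, Section 7.3.3 allows earlier scans when clinically indicated and uses data from scans done at other times, and patients on modified follow-up stay in. The shift is small beside intervals this wide. What stands is that the only written evaluability rule depends on remaining on study, and nothing clearly replaces it.

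**On resection.** A reader might infer that the plan intends to count resection as complete response, or that the pooled rate is certainly biased upward. Neither is supported. RECIST 1.1 is adopted by name, and whether it settles the handling of removed lesions cannot be checked from these documents. Objective 2.4 concerns the anti-tumor effects of the transferred cells, which surgery is not. The 9.4 remark about imaging concerns the surgical plan and does not rule out a later scan before surgery. Group rates are also shown separately, so a rate driven by surgery would be visible. What stands is that the protocol's own definitions are silent, and that dilution remains even if nobody scores surgery as response.

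**Conclusion.** The concern holds as two unstated rules, and it is minor. The literal 8.0 rule can only raise the response rate or leave it unchanged: from 20% to between 21% and 30% for three responders in a group of 15 with one to five leaving unscanned. Pooling Group C dilutes the rate if resection is not scored as response (20% to 13% in the example) and adds 2.2 points per patient if it is. Running the diluted 13% and the all-15-scored 47% together as one range of bias would overstate the point, since the two ends come from opposite conventions and the upper end needs every Group C patient scored as complete response.

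The separate A and B rates are untouched by the resection question. Efficacy is listed as tertiary in Section 9.1, response is summarized descriptively, and neither the sample size nor any halting rule uses it. The sizes rest on assumed counts; the gaps in the text do not.

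**What to change.** - **8.0 and 9.3.2:** for the groups analyzed for response, define the denominator as all patients with at least one infusion, matching the safety population in 9.3.1. Count those with no post-baseline assessment as non-responders.
- **8.1:** state that surgical removal of a lesion is not a response.
- **9.3.2:** report the pooled response rate for Groups A and B only, with A and B also shown separately. Describe Group C by the progression-free and overall survival already planned, stating that progression after resection is judged by new lesions.
- **Editorial:** correct the reference to Section 8.4.

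The cost is wording only, with no added visits, scans or data. The reported rate may be slightly lower, and the pooled n is at most 30. With zero responders the upper 95% limit is 1 − 0.025^(1/30) = 11.6%, against 1 − 0.025^(1/45) = 7.9% with all 45. A limit remains: Group A is infused during continuing chemotherapy (Section 5.2), so a pooled A and B rate does not isolate T-cell activity. That is why the two rates should stand beside it.
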